9.2. Treatment Administration

This study involves an evaluation of ixekizumab 80 mg administered by prefilled syringe during the treatment period. For the single-dose phase, all patients will receive a single dose of 80 mg given as one 80 mg SC injection at Week 0 (Visit 2) and will then be observed for a 20-week period. For the multiple-dose phase, all patients will receive a 160 mg SC starting dose (2 injections) and will then be randomized at a 1:1 ratio to 1 of 2 dose groups via a computer-generated random sequence using an interactive web-response system (IWRS): one group will receive 80 mg SC Q2W starting on Day 15, and the other group will receive 80 mg SC Q4W starting on Day 29 for the duration of the 8-week treatment period. All patients in the multiple-dose phase will be followed for an additional 20-week observation period after the treatment period completes.

Injections will be administered at the site by the clinical staff.

Administration: A dose of investigational product will consist of SC injection(s) of investigational product. Possible injection sites include the abdomen, thigh, and upper arm. The injection site should not be in a psoriatic lesion and should be rotated to another area for subsequent doses.

Allow the prefilled syringe containing the drug product to equilibrate to room temperature for approximately 30 minutes. Do not return syringe to the refrigerator.

The investigator or designee is responsible for:

- explaining the correct use of the investigational agent to the site personnel,
- verifying that instructions are followed properly,
- maintaining accurate records of investigational product dispensing and collection,
- and returning all unused medication to Lilly or its designee at the end of the study.

Note: In some cases, sites may destroy the material if, during the investigator site selection, the evaluator has verified and documented that the site has appropriate facilities and written procedures to dispose clinical trial materials.

Patients will be instructed to contact the investigator as soon as possible if he or she has a complaint or problem with the investigational product so that the situation can be assessed. See Section 10.4.5 for more details.

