Urinalysis	X	PreD			X					X										X			X
Serum for anti-ixekizumab antibody		PreD			X		X		X									X			X		X
Urine pregnancy test ^m	X	PreD								X										X			X

Abbreviations: C-SSRS = Columbia-Suicide Severity Rating Scale; ECG = electrocardiogram; h = hour(s); PASI = Psoriasis Area and Severity Index; PK = pharmacokinetics; PPD = purified protein derivative; PreD = prior to dose; Q2W = every 2 weeks; Q4W = every 4 weeks; QIDS-SR₁₆ = Quick Inventory of Depressive Symptomatology–Self Report, 16 item; QTF = QuantiFERON[®]-TB Gold test; sPGA = static Physician’s Global Assessment; TB = tuberculosis; T-SPOT = T-SPOT[®].TB test; V = visit.

Notes: Patients who withdraw from the treatment phase will have an early treatment discontinuation visit with procedures performed as shown for Visit 16. Visits denoted by a letter after the visit number are visits at which the patient will visit the study site for serum ixekizumab sampling only. No other tests will be performed at these visits.

- a Visit 1 procedures may be conducted over more than 1 day as long as all tasks are completed within the allowable visit tolerance (at least 3 days should be allowed for receipt of laboratory test results).
- b Weight may be recorded at other visits as clinically indicated.
- c Sitting blood pressure, respiratory rate, and pulse rate are to be obtained at approximately the same time as ECG measurements or plasma ixekizumab blood sampling. When multiple assessments are scheduled for the same time point, the order of completion should be ECG, vital signs, and then blood sampling.
- d Body temperature should be taken only for patients in the Q2W group at this visit because patients in the Q4W group do not receive study drug at this visit.
- e Patients with documentation of a negative test result within 3 months prior to baseline (Week 0; Visit 2) do not need a TB screen at Visit 1.
- f See Section 10.4.3.5 for detailed description of PPD/QTF or T-SPOT testing.
- g To account for diurnal variations, ECGs should be performed at approximately the same time of day as the Visit 2 predose ECG (±2 hours).
- h Additional ECGs may be performed as clinically indicated.
- i Each blood draw should be collected at approximately the same time of day as the initial sample taken prior to dose administration at Week 0 (Visit 2).

- j When PK samples are scheduled at the same visits as dose administrations, then the PK sample should be taken pre-dose.
- k Only for the Q2W dosing regimen.

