5. STUDY DESIGN

Study RHBN is a Phase 1, multicenter, open-label, single- and multiple-dose outpatient study in up to 45 patients with psoriasis. A 160 mg SC starting dose (Week 0) followed by an 80 mg SC dose Q2W or Q4W was evaluated as an induction dosing regimen over 12 weeks of treatment in global pivotal Phase 3 studies in patients with psoriasis (Studies RHAZ, RHBA, and RHBC). In this study, the PK profile and safety/tolerability of ixekizumab 80 mg will be assessed initially in the single-dose phase. Thereafter, the induction dosing regimens evaluated in the pivotal Phase 3 studies will be evaluated in the multiple-dose phase for this Phase 1 study in China.

For the single-dose phase, patients will receive a single dose of ixekizumab 80 mg SC on Day 1 and will be assessed at regular visits for 20 weeks. Patients completing the single-dose phase have the option of enrolling in the multiple-dose phase after completing the final visit in the single-dose phase. Patients will remain at the site for a minimum of 4 hours postdose.

The multiple-dose phase can be initiated once 6 patients have completed the Week 6 (Day 43) visit in the single-dose phase and safety data collected through 6 weeks postdosing from these patients have been reviewed. After review of these safety data, an agreement on initiation of the multiple-dose phase will be made by the investigator and sponsor.

In the multiple-dose phase, patients will be administered a starting dose of ixekizumab 160 mg SC on Day 1 and will then be randomized into 1 of 2 dosing regimens for the 8-week treatment period: (1) 80 mg SC Q2W (at Weeks 2, 4, 6 and 8) or (2) 80 mg SC Q4W (at Weeks 4 and 8). After Week 8, patients will be assessed at regular visits for an additional 20 weeks. Patients will remain at the site for a minimum of 4 hours after the first dose and for 2 hours after subsequent doses.

Figure 1 and Figure 2 illustrate the study design for the single-dose phase and multiple-dose phase, respectively.

Single-Dose Phase

Abbreviations: D = day; SC = subcutaneous; V = visit; W = week. Note: Patients who complete Visit 14 of the single-dose phase are eligible for participation in the multiple-dose phase.

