9.3 Pharmacokinetic Assessment

9.3.1 Pharmacokinetic Analysis

Noncompartmental methods will be applied using a validated software program (Phoenix WinNonlin Version 6.4 or later) to analyze the serum concentrations of ixekizumab and determine the PK parameters of ixekizumab.

Single-Dose Phase

Following the 80 mg in the single dose phase, the following PK parameters will be determined, when possible:

Statistical Analysis Plan Version 2 Covance Clinical Study No. 8346599

Parameter	Units	Definition
AUC(0-t _{last})	µg.day/mL	area under the concentration versus time curve from time zero to time t, where t is the last time point with a measurable concentration
AUC(0-∞)	μg.day/mL	area under the concentration versus time curve from zero to infinity
%AUC(tlast-∞)	%	percentage of $AUC(0-\infty)$ extrapolated
C _{max}	μg/mL	maximum observed drug concentration
t _{max}	day	time of maximum observed drug concentration
t _{last}	day	time of last observed drug concentration
t _{1/2}	day	half-life associated with the terminal rate constant (λz) in non- compartmental analysis
CL/F	L/h	apparent total body clearance of drug calculated after extra-vascular administration
V_Z/F	L	apparent volume of distribution during the terminal phase after extra-vascular administration
V _{SS} /F	L	apparent volume of distribution at steady state after extra-vascular administration

Multiple-Dose Phase

Serum concentrations of ixekizumab following single dosing of 160 mg on Day 1 (i.e. up to 14 days post the first dose and prior to the second ixekizumab dose), will be used to determine the single dose PK parameters and will be a subset of the parameters listed above that can be calculated based on only 14 days worth of sampling. Serum concentrations of ixekizumab from Week 8 following the last dose of repeated dosing of ixekizuamb will be used to determine the following multiple-dose PK parameters, when possible:

Parameter	Units	Definition
AUCτ	μg.day/mL	area under the concentration versus time curve during one dosing interval
C_{max}	µg/mL	maximum observed drug concentration
t _{max}	day	time of maximum observed drug concentration
t _{1/2}	day	half-life associated with the terminal rate constant (λz) in non- compartmental analysis
CL/F	L/h	apparent total body clearance of drug calculated after extra-vascular administration
V_Z/F	L	apparent volume of distribution during the terminal phase after extra-vascular administration

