V_{SS}/F	L	apparent volume of distribution at steady state after extra-vascular administration

Additional PK parameters may be calculated, as appropriate. The software and version used for the final analyses will be specified in the CSR. Any exceptions or special handling of data will be clearly documented within the final study report.

Formatting of tables, figures and abbreviations will follow the Eli Lilly Global PK/PD/TS Tool: NON-COMPARTMENTAL PHARMACOKINETIC STYLE GUIDE. The version of the tool effective at the time of PK analysis will be followed.

General PK Parameter Rules

- Actual sampling times will be used in the final analyses of individual PK parameters, except for non-bolus pre-dose sampling times which will be set to zero. For non-bolus, multiple dose profiles, the pre-dose time will be set to zero unless a time deviation falls outside of the protocol blood collection time window which is considered to impact PK parameter derivation.
- C_{max} and t_{max} will be reported from observed values. If C_{max} occurs at more than one time point, t_{max} will be assigned to the first occurrence of C_{max}.
- AUC parameters will be calculated using a combination of the linear and logarithmic trapezoidal methods (linear-log trapezoidal rule). The linear trapezoidal method will be applied up to t_{max} and then the logarithmic trapezoidal method will be used after t_{max}. The minimum requirement for the calculation of AUC will be the inclusion of at least three consecutive serum concentrations above the lower limit of quantificati on (LLOQ), with at least one of these concentrations following C_{max}.
- Half-life (t¹/₂) will be calculated, when appropriate, based on the apparent terminal log-linear portion of the concentration-time curve. The start of the terminal elimination phase for each patient will be defined by visual inspection and generally will be the first point at which there is no systematic deviation from the log-linear decline in serum concentrations. Half-life will only be calculated when a reliable estimate for this parameter can be obtained comprising of at least 3 data points. If t¹/₂ is estimated over a time window of less than 2 half-lives, the values will be flagged in the data listings. Any t¹/₂ value excluded from summary statistics will be documented in the footnote of the summary table.
- A uniform weighting scheme will be used in the regression analysis of the terminal loglinear portion of the concentration-time curve.

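### The first-dose (160 mg) noncompartmental window stops at 14 days in both arms, so two scheduled Q4W samples taken before the second dose enter no specified parameter

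*SAP*

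**What the plan says.** SAP 9.3.1, Multiple-Dose Phase, specifies two sets of noncompartmental parameters.

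- **First dose.** Concentrations "up to 14 days post the first dose and prior to the second ixekizumab dose" are used, and the parameters reported are a "subset of the parameters listed above that can be calculated based on only 14 days worth of sampling". The rule is the same for both arms.
- **Last dose.** Concentrations from Week 8 onward are used.

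The arms differ in when the second dose falls. Protocol 9.2 starts Q2W dosing on Day 15, while "the other group will receive 80 mg SC Q4W starting on Day 29". SAP 5 agrees: "80 mg SC Q4W (at Weeks 4 and 8").

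Protocol Attachment 2 marks a PK sample on Day 22 and on Day 29 without restriction by arm. Footnote k, "Only for the Q2W dosing regimen", is attached to the Day 43 sample only. Footnote j reads "When PK samples are scheduled at the same visits as dose administrations, then the PK sample should be taken pre-dose", so the Day 29 sample precedes the dose given that day.

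The General PK Parameter Rules in SAP 9.3.1 add two conditions: "Half-life will only be calculated when a reliable estimate for this parameter can be obtained comprising of at least 3 data points", and if half-life is "estimated over a time window of less than 2 half-lives, the values will be flagged in the data listings".

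**The concern.** The SAP treats the 14-day limit and the time before the second dose as one window. That is true for Q2W and untrue for Q4W, where the first-dose interval is 28 days. In Q4W the Day 22 and pre-dose Day 29 samples are still first-dose data, but they fall after the 14-day cut and before the Week 8 window.

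The SAP chose to report first-dose parameters for 160 mg. With a half-life near 13 days, 14 days of sampling leaves little terminal phase to fit. The SAP's own half-life rule may then bar the estimate, and AUC(0-∞) and CL/F go with it. Where the rule is met, the estimate is poor. The samples that would help are already scheduled.

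**Working it through.** **1. Windows from the schedule.** First-dose interval = day of second dose − Day 1.

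- Q2W: 15 − 1 = 14 days, which reproduces the SAP window.
- Q4W: 29 − 1 = 28 days, which does not match it.

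**2. Check on the reading of the schedule.** The PK row of Attachment 2 gives 1 pre-dose sample, 7 on Days 3 to 29, 1 on Day 43 (Q2W only) and 13 from Day 57. That is 1 + 7 + 1 + 13 = 22 samples, and 22 × 4 mL = 88 mL. Both figures match Attachment 4.

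**3. Samples in the Q4W first-dose interval.** Post-dose times are 2, 4, 7, 10, 14, 21 and 28 days. The 14-day limit keeps the first 5 of the 7.

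**4. Share of AUC(0-∞) observed.** This assumes one compartment with first-order absorption. Inputs from Protocol 5.1 are a half-life of about 13 days and a tmax of about 4 to 7 days.

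- ke = ln 2 / 13 = 0.0533 per day.
- ka solves tmax = ln(ka/ke)/(ka − ke).
- Observed share at T = 1 − [e^(−ke·T)/ke − e^(−ka·T)/ka] / [1/ke − 1/ka].

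For tmax 4 and T = 14: 1/ke = 18.755, 1/ka = 1.438, and the unobserved part is 8.890 / 17.317 = 0.513. The observed share is therefore 0.487.

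| tmax (d) | ka (per d) | 14 days | 28 days |
|---|---|---|---|
| 4 | 0.695 | 48.7% | 75.7% |
| 5.5 | 0.435 | 46.0% | 74.4% |
| 7 | 0.300 | 42.7% | 72.7% |

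Across the ±2-day window of the Day 29 visit (26 to 30 days), the later figure runs from 70% to 78%.

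**5. Chance of having enough points for a half-life.** Simulation of 20,000 profiles per case at the scheduled times, with lognormal residual error and no between-patient variability. The error sizes are assumptions. The proxy for the SAP rule is at least 3 samples strictly after the observed peak.

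| Residual error | Window | tmax 4 | tmax 5.5 | tmax 7 |
|---|---|---|---|---|
| 5% | 14 d | 91% | 41% | 4% |
| 5% | 28 d | 100% | 100% | 100% |
| 10% | 14 d | 77% | 42% | 13% |
| 10% | 28 d | 100% | 100% | 98% |
| 15% | 14 d | 70% | 40% | 18% |
| 15% | 28 d | 99.7% | 98% | 94% |

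If the peak sample itself may count, the 14-day figures at 10% error are 98%, 89% and 68%. Adding 30% between-patient variability to ka and ke, with the peak not counted and 10% error, gives 72%, 44% and 20% at 14 days against 100%, 99% and 93% at 28 days.

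**6. Precision where the rule is met.** Settings: 10% error, tmax 4, last three points, linear-up/log-down AUC, predicted last concentration. Values are median (5th to 95th percentile).

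| | 14 days | 28 days |
|---|---|---|
| Half-life (true 13 d) | 14.4 (8.7–40.6) | 13.0 (9.9–18.8) |
| AUC(0-∞) / true | 1.05 (0.78–2.29) | 0.99 (0.90–1.15) |

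Non-negative slopes (0.7% of the 14-day profiles) were excluded. A tmax of 4 is the case most favourable to the 14-day window. With tmax 5.5 to 7, the 14-day half-life is biased upward, with a median of about 15 to 30 days depending on tmax and on whether the peak counts. The 28-day median stays near 13 days.

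**The case against.** The strongest reply is that 14 days is a deliberate scope. Both arms get the same 160 mg dose and are treated alike until Day 15, so a common window keeps first-dose parameters comparable, and the SAP openly accepts that only some parameters will be available. Comparability is a good reason for Cmax, tmax and a partial AUC. But the SAP does not give that reason, and its wording equates two conditions that differ in Q4W. Comparability also does not require discarding later Q4W data for half-life.

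Other points, and what stands of each:

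- SAP 9.3.1 allows additional PK parameters as appropriate, so a 28-day Q4W analysis could be added. That is optional, names nothing and leaves the stated window unchanged.
- The samples are still listed and plotted, and Protocol 11.2.4 allows population PK. True; the gap concerns specified noncompartmental parameters only.
- Q2W samples on Days 22, 29 and 43 also enter no specified parameter. True, but they follow the second dose and cannot belong to a first-dose profile.
- The half-life rule does not say that its three points must follow the peak, and it relies on visual inspection. This stands: how often half-life is barred depends on how the terminal phase is chosen. The imprecision does not go away.
- Protocol 11.2.4 asks for parameters after the single dose and after the last dose; the 160 mg first-dose set is an SAP addition. This stands and limits the importance of the point.

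**Conclusion.** The point holds, and it is minor. The mismatch follows from the schedule alone: the SAP window fits Q2W and cuts the Q4W first-dose interval in half, leaving 2 of 7 post-dose samples outside every specified noncompartmental parameter.

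The size rests on the assumed one-compartment model and error levels. The unobserved part of AUC(0-∞) is 51–57% at 14 days against 24–27% at 28 days, and half-life is much less precise on the shorter window.

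The reach is small: about 10 planned completers, descriptive statistics only, and no effect on the 80 mg single-dose or Week 8 parameters, which mainly carry the primary objective.

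**What to change.** In SAP 9.3.1, define the first-dose window as running up to and including the pre-dose sample of the second dose: Day 15 for Q2W, Day 29 for Q4W. Then:

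- keep Cmax, tmax and a partial AUC over 0 to 14 days on the common window in both arms;
- use data through Day 29 for Q4W half-life, AUC(0-∞) and CL/F, retaining the flag for spans under 2 half-lives and reporting the percentage extrapolated;
- state that AUC(0-tlast) after the first dose is not compared between arms, because the windows differ.

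Optionally, add one pooled first-dose column (about n = 20) for the common-window parameters. If 14 days was meant for both arms, the SAP should say so and give the reason.

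The cost is wording; no sample or visit is added. The gain has limits. A Q4W half-life over Days 15 to 29 spans 14/13 = 1.1 half-lives and stays flagged (against 7/13 = 0.5 for Days 8 to 15), and about a quarter of AUC(0-∞) is still extrapolated.

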7. SAMPLE SIZE JUSTIFICATION

Up to 45 patients (15 patients for the single-dose phase and 30 patients for the multiple-dose phase) will be enrolled to target that 8 patients complete the single-dose phase and 20 patients (10 for each dosing regimen) complete the multiple-dose phase.

This study has been designed to meet the primary objective of assessing the PK of a single dose and multiple doses of ixekizumab in Chinese patients with psoriasis. The sample size was chosen to meet Chinese regulatory requirements and to provide sufficient data to evaluate the objectives and is not intended to achieve any prior statistical requirements.

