• A concentration average will be plotted for a given sampling time only if 2/3 of the individual data at the time point have quantifiable measurements that are within the sampling time window specified in the protocol or ± 10%. An average concentration estimated with less than 2/3 but more than 3 data points may be displayed on the mean concentration plot if determined to be appropriate and will be documented within the final study report.

Treatment of Outliers during Pharmacokinetic Analysis

Application of this procedure to all PK analyses is not a requirement. Rather, this procedure provides justification for exclusion of data when scientifically appropriate. This procedure describes the methodology for identifying an individual value as an outlier for potential exclusion, but does not require that the value be excluded from analysis. The following methodology will not be used to exclude complete profiles from analysis.

Data within an Individual Profile

A value within an individual profile may be excluded from analysis if any of the following criteria are met:

- For PK profiles during multiple dosing, the concentration of the pre-dose sample exceeds all measured concentrations for that individual in the subsequent post-dose samples.
- For PK profiles during single dosing of non-endogenous compounds, the concentration in a pre-dose sample is quantifiable.
- For any questionable datum that does not satisfy the above criteria, the profile will be evaluated and results reported with and without the suspected datum.

Data between Individual Profiles

- 1. If n < 6, then the dataset is too small to conduct a reliable range test. Data will be analyzed with and without the atypical value, and both sets of results will be reported.
- 2. If n≥6, then an objective outlier test will be used to compare the atypical value to other values included in that calculation:
 - a. Transform all values in the calculation to the logarithmic domain.
 - b. Find the most extreme value from the arithmetic mean of the log transformed values and exclude that value from the dataset.
 - c. Calculate the lower and upper bounds of the range defined by the arithmetic mean $\pm 3^{*}$ SD of the remaining log-transformed values.
 - d. If the extreme value is within the range of arithmetic mean ± 3 *SD, then it is not an outlier and will be retained in the dataset.

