e. If the extreme value is outside the range of arithmetic mean ± 3 *SD, then it is an outlier and will be excluded from analysis.

If the remaining dataset contains another atypical datum suspected to be an outlier and $n \ge 6$ following the exclusion, then repeat step 2 above. This evaluation may be repeated as many times as necessary, excluding only one suspected outlier in each iteration, until all data remaining in the dataset fall within the range of arithmetic mean ± 3 *SD of the log-transformed values.

Reporting of Excluded Values

Individual values excluded as outliers will be documented in the final report. Approval of the final report will connote approval of the exclusion.

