9.3.2 Pharmacokinetic Statistical Methodology

Descriptive statistics of PK parameters will be presented for each dose regimen (single-dose, Q2W multiple-dose, and Q4W multiple-dose) separately.

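### The between-patient PK outlier limit of ±3 SD ignores group size: if run on every group it would flag a valid value in about 25% (n=8), 22% (n=10) or 19% (n=15) of clean groups, and acting on those flags understates variability

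*SAP*

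**What the plan says.** SAP 9.3.1, under treatment of outliers between individual profiles, treats fewer than six values as too few for a reliable range test and asks for results with and without the atypical value. For six or more, "then an objective outlier test will be used to compare the atypical value to other values included in that calculation". On the log scale the analyst must first "Find the most extreme value from the arithmetic mean of the log transformed values and exclude that value from the dataset". The next instruction, which uses only the values left over, is "Calculate the lower and upper bounds of the range defined by the arithmetic mean", with the limits placed 3 SD to either side. If the removed value lies outside them, "then it is an outlier and will be excluded from analysis". If another value is suspected and at least six remain, "This evaluation may be repeated as many times as necessary, excluding only one suspected outlier in each iteration".

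The preamble to the same section is softer. It says the procedure need not be applied to every PK analysis, that it identifies values for possible exclusion without requiring exclusion, and that it may not be used to drop whole profiles. Excluded values are to be documented in the final report.

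The results affected are the primary ones. SAP 9.3.2: "Descriptive statistics of PK parameters will be presented for each dose regimen (single-dose, Q2W multiple-dose, and Q4W multiple-dose) separately". SAP 9.1 adds the geometric mean and geometric CV for AUC and Cmax. On group size, the completer numbers in SAP 7 are given as "target that 8 patients complete the single-dose phase and 20 patients (10 for each dosing regimen) complete the multiple-dose phase". The enrolment ceiling in the same section reads "Up to 45 patients (15 patients for the single-dose phase and 30 patients for the multiple-dose phase) will be enrolled". Neither document gives an error rate for the outlier test.

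**The concern.** A 3 SD limit suggests a rare event: for one normal value with known mean and SD, the two-sided probability is 0.27%. Two features of this rule break that link. The SD comes from only n-1 values, so the reference distribution is a heavy-tailed t with n-2 degrees of freedom. And the value tested is not a pre-named patient but the most extreme of n, so the rule in effect makes n comparisons. Both effects depend on n; the multiplier does not.

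PK is the primary objective and its analysis is entirely descriptive. A valid extreme value removed under this rule lowers the reported geometric CV and shifts the geometric mean, and the distortion of the CV always runs downward. At n≥6, the size of every planned group, the SAP does not require the summary with the value kept in.

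**Working it through.** The plan states no figure to reproduce, so the check derives the operating characteristics of the rule as written.

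**Inputs.** Limit 3, applied to the most extreme value after its removal, for n≥6 (SAP 9.3.1). Target completers 8, 10 and 10; maximum enrolment 15 and 30, which is 15 per multiple-dose regimen under the 1:1 randomisation in Protocol 9.2 (SAP 7). Assumptions: log-normal values, independent patients, no true outliers, test run on every group. The flag rate does not depend on the true mean or SD.

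**Flag rate.** For any one patient, the deviation from the mean of the others, divided by the SD of the others, is distributed as sqrt(n/(n-1)) × t with n-2 df. The value farthest from the overall mean is also the one with the largest such ratio. So, very nearly, flag rate = n × P(|t(n-2)| > 3/sqrt(n/(n-1))):
- n=8: 3/1.069 = 2.806; two-sided p on 6 df = 0.0309; × 8 = 0.247
- n=10: 3/1.054 = 2.846; p on 8 df = 0.0216; × 10 = 0.216
- n=15: 3/1.035 = 2.898; p on 13 df = 0.01245; × 15 = 0.187

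Simulation of 1,000,000 clean groups per size gives 24.8%, 21.6% and 18.6%. At n=6, the smallest size allowed, it is 31%.

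**Any of three regimens, one parameter** (groups treated as independent): 1 - (1-0.248)(1-0.216)² = 0.54 at 8/10/10; 1 - (1-0.186)³ = 0.46 at 15/15/15.

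**Effect if every first-pass flag is acted on** (simulation, true SD = 1):

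| n | Mean log-SD, before → after | Average log-variance understated | Fall in log-SD within flagged groups |
|---|---|---|---|
| 8 | 0.965 → 0.873 | 15% | 39% |
| 10 | 0.972 → 0.903 | 12% | 33% |
| 15 | 0.983 → 0.938 | 8% | 25% |

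The documents give no PK variability, so the CV scale needs an assumption. With a true CV of 30%, the mean geometric CV in flagged groups falls from 29% to 17.5% (n=8), 29% to 19% (n=10) and 29.5% to 22% (n=15). With 50%, it falls from 49% to 29%, 32% and 36%. Over all groups, at a true CV of 30%, the average falls from 29.0% to 26.2%, 29.2% to 27.1% and 29.5% to 28.1%.

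**Repetition.** If the test is repeated while n≥6, 7% of clean groups at n=8 and 5% at n=10 lose two or more values.

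**Size-dependent limit.** Setting the flag rate to 5% gives k(n) = t(1 - 0.05/(2n); n-2 df) × sqrt(n/(n-1)): 4.115 × 1.069 = 4.40 at n=8; 3.833 × 1.054 = 4.04 at n=10; 3.584 × 1.035 = 3.71 at n=15. Simulated flag rates with these limits are 5.0% at each size, and the average log-variance loss drops to about 4%, 3% and 3%.

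**The case against.** A reader might infer that the plan will drop a valid patient from a quarter of its groups. The documents do not support that. The preamble makes both running the test and acting on it discretionary, the test starts from a value somebody already finds atypical, and whole profiles may not be excluded. The actual removal rate therefore cannot be derived; the figures above are upper bounds at each group size, for a single value in a single calculation.

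A reader might also infer that Chinese patients will look less variable than the global population. Protocol 5.2 does foresee a comparison with non-Chinese patients, but the documents do not say how outliers were handled in the global data. If the same procedure was used there, part of the bias is shared.

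Two further points are fair. The PK population in SAP 8 is dosed patients with evaluable data, not completers, so groups may be nearer 15, where the rate is 19%. And because exclusions are documented and all databased data are listed, a reader could rebuild the full summary.

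Discretion does not cure the defect, however. The SAP offers the test as objective justification for exclusion, and a test that flags a clean group one time in four or five is weak justification. Steps 2 and 2e are worded as mandatory, and nothing defines when a value counts as atypical. Documenting an exclusion is not the same as reporting the summary with the value kept.

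**Conclusion.** The concern stands as a calibration fault in the outlier limit, not as a prediction of how many values will be lost. At the planned sizes, ±3 SD flags clean groups roughly four to five times as often as a conventional 5% rule would (24.8/5 and 21.6/5), and still nearly four times as often at 15 per regimen (18.6/5). To the extent that flags are acted on, the geometric CV is biased downward, by up to the amounts tabulated. This rests on log-normality, independence between patients and groups (patients may enter both phases, so the three-regimen figures are approximate), and the test being run on every group. The fault should be corrected because it acts on the primary descriptive outputs and is cheap to remove; it does not threaten the study.

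**What to change.** Either of two changes to SAP 9.3.1, made before the PK analysis:

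1. In steps 2c to 2e, replace 3 with k(n) = t(1 - 0.05/(2n); n-2 df) × sqrt(n/(n-1)), which is 4.40 at n=8, 4.04 at n=10 and 3.71 at n=15, and allow one pass only. The 5% rate is a conventional choice, not a figure from the documents.
2. Keep ±3 SD purely as a flag. Make the PK summary with all values the main result, and report the summary without the flagged value beside it. This needs no choice of error rate and extends to larger groups the dual reporting already required below six.

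The cost is a few lines of SAP text and, for the first option, one line of code; no new data are needed. The downside is that moderately aberrant values stay in the main summary more often.
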